9.3 Definition of Populations

Forty women with DSM-IV diagnoses of premenstrual dysphoric disorder (PMDD) will be selected for the study. Before entering the study, patients will be screened using standardized questionnaires and the Structured Clinical Interview for Diagnosis (SCID), complete daily mood self-ratings for two months (required to confirm a DSM-IV diagnosis) and visit our clinic weekly for Hamilton, Beck, atypical and mania ratings to observe individual changes in symptoms over the menstrual cycle that include symptoms of anxiety, irritability, mood lability and physical discomfort. Eligibility, inclusion and exclusion criteria are listed below. All subjects with valid baseline and at least one post baseline measurement will be included in the analysis.

PMDD Subjects: Eligibility, Inclusion and Exclusion Criteria:

Inclusion criteria

- 1) Age: 18-45 years.
- 2) Women with regular ovulatory menstrual cycles 26-32 days in length (for at least the previous six months).
- 3) A history of a depressive (but not bipolar) mood disorder, but not an ongoing episode (symptom free for the last 12 months).
- 4) Patients must meet DSM-IV criteria for Premenstrual Dysphoric Disorder (that includes irritability).
- 5) Objective ratings: mean of HRSD total scores across evaluation weeks 1-8 \leq 7 for follicular phase (day 5-10 of cycle after menses); mean of total HRSD scores across evaluation weeks 1-8 \geq 14 for premenstrual (luteal) phase (6 days prior to onset of menses onward).
- 6) Subjective ratings: mean of Beck Depression Inventory total scores across evaluation weeks 1-8 $<$ 10 follicular phase; \geq 10 premenstrual (luteal) phase.
- 7) Daily ratings: minimal symptoms (mean less than 50 mm on 100mm scale) follicular phase; at least a 30% increase in mean affective symptom ratings, premenstrual (luteal) phase.
- 8) By clinical assessment and ratings, the patient has reported a history (for at least the last six months) of recurrent, moderate to severe premenstrual mood symptoms that impair some aspect of social or occupational functioning and that remit within a few days after the onset of menses. This pattern is prospectively documented with subjective daily mood ratings (DMR – visual analogue scale) during at least two consecutive symptomatic cycles. Symptom severity will also be documented with objective and subjective ratings over that time. Patients must demonstrate a consistency of symptoms and a long enough duration of symptoms (7-10 days) to allow for study.
- 9) Subjects willing to endure the rigors of a long-term (up to 6 months) research study.

Exclusion Criteria

- 1) Subjects with significant medical illness including hepatic (abnormal liver function tests), neurological, renal, cardiac, pulmonary, hematologic, gastrointestinal, or metabolic disorders.

- 2) Subjects who are lactating, are within 6 months postpartum, or have an irregular sleep- wake cycle, e.g., from having very young children in the home.
- 3) Subjects who are using hormonal contraception (within six months prior to the study).
- 4) Subjects using medication that may affect outcome measures of mood, circadian rhythms or hormone levels (6-sulphatoxy-melatonin, estradiol, progesterone, FSH, LH, prolactin) within one month of initiating the study or anytime during the study. Such medications include OTC medication (excluding Tylenol), antidepressants, anti-anxiety, antihypertensive, beta blockers, and asthma medications. Vaccinations, vitamins/mineral supplements (excluding St. John's Wart, melatonin and valerian) and/or short course antibiotics will not be considered exclusionary.
- 5) Subjects with significant psychiatric disorder (schizophrenia, bipolar disorder, anxiety disorders, eating disorders, personality disorders, sleep disorders). An ongoing major depressive episode within the last year is reason for exclusion, although a previous history of a depressive episode is not (using DSM-IV diagnostic criteria for a major depressive episode).
- 6) Subjects with a recent history (within the past year) of drug or alcohol abuse.
- 7) Subjects with a history of anemia, kidney, cardiopulmonary, metabolic, liver or thyroid disease within one year of participation (per patient-reported medical history).
- 8) Subjects with irregular menstrual cycles (cycle lengths vary greater than 3 days or who fail to ovulate for 2 consecutive months).
- 9) Subjects unlikely to cooperate with the requirements of the study.
- 10) Subjects needing frequent or continuous use of any medication or drugs that may affect outcome measures, including alcohol (>1 drink daily) and nicotine (>5 cigarettes daily).
- 11) Subjects whose prospective DMR ratings do not show cyclic variation in association with the menstrual cycle (as per inclusion criteria).
- 12) Subjects with an irregular sleep schedule, *extreme chronotypes* or a sleep-wake cycle that does not correspond to the environmental light-dark cycle (e.g., subjects within 2 weeks of transmeridian travel, night shift workers, or those with significant advanced or delayed sleep phase syndromes).

9.4 Interim Analyses and Stopping Rules

This study will be stopped prior to its completion if: (1) the intervention is associated with adverse effects that call into question the safety of the intervention; (2) difficulty in study recruitment or retention will significantly impact the ability to evaluate the study endpoints; (3) any new information becomes available during the trial that necessitates stopping the trial; or (4) other situations occur that might warrant stopping the trial.

No interim analysis is planned.

9.5 Outcomes

9.5.1 Primary Outcome

- Treatment-Related Mood Rating Changes from Baseline (month 2) to post intervention (months 3,5) :
Mood ratings include Hamilton Rating Scale for Depression (HRSD), Beck Depression Inventory (BDI), atypical depression symptoms as part of the Structured Interview Guide for the Hamilton Depression Rating Scale, Seasonal Affective Disorders version (SIGH-SAD), Beck Anxiety Inventory (BAI), mania ratings, the Psychological General Well-Being Index (PGWI) and daily mood self-ratings (DMR) that include core PMDD symptoms of anxiety and irritability as required during diagnostic evaluation, before, during and after each wake and light intervention at the same time of day (between 15:00-17:00 h). To assess more acute effects on mood that may occur more rapidly during the wake interventions, subjects will complete DMRs twice daily beginning the evening before the wake therapy intervention and continuing until the morning after the recovery night of sleep.
- Treatment-Related Urinary 6-sulfatoxymelatonin (6-SMT) Changes from Baseline (month 2) to post intervention (months 3,5) :
6-SMT is a principal melatonin metabolite that is abundant in urine, well correlated with plasma melatonin, and serves as an excellent marker for circadian phase response.
- Treatment-related changes in objective and subjective sleep measures:
Using actigraphy, we will obtain objective measures of the sleep/wake cycle to ensure appropriate sleep/wake times during wake therapy, and during the light interventions as it is an important biological rhythm with which to compare the intervention-induced melatonin rhythm changes. To assess subjective sleep quality, we will use the Pittsburgh Sleep Quality Index (PSQI) and a visual analogue scale.

9.5.2 Secondary Outcomes

- Effects of expectation, morningness/eveningness and seasonality on primary outcome measures:
Prior to entering the study, subjects will complete expectation forms measuring their expectation for change with the interventions (100 mm line from "much worse" to "much better") as well as Horne-Östberg scales to assess morningness and eveningness, as these variables may mediate or moderate primary outcome measures. To determine whether seasonality affects outcome, subjects will complete the Seasonal Pattern Assessment Questionnaire (SPAQ).
- Treatment-related changes from baseline (month 2) and 1-2 days post intervention (months 3,5) in reproductive hormones:
We will obtain overnight urinary samples for estradiol, progesterone, gonadotropins and prolactin (obtained at the same time of 6-SMT overnight collections in baseline and intervention months).
- Subjective visual analog scale-based global assessment of treatment effectiveness:

Following both treatment interventions, subjects will complete a visual analog scale-based global assessment of treatment effectiveness.

- Subjective assessment of side effects to treatment: collected 1-2 days post intervention (months 3,5)

Following each treatment interventions, subjects will complete an assessment of side effects using the Side Effects Checklist.

As delineated in our Data and Safety Monitoring Plan, the Independent Monitoring Committee will meet on an annual basis to review outcome data. The committee will be masked to a participant's intervention group assignment.

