6.2.2 Enrollment, Baseline, and/or Randomization

Baseline Assessments

In accordance with the Schedule of Evaluations (section 6.1 above), baseline measures will be collected in Evaluation Month 2 as follows:

- Hamilton: The Hamilton Rating Scale for Depression (HRSD)⁵⁶ (as a validated objective, interview-based assessment of depression). Atypical depression symptoms as part of the Structured Interview Guide for the Hamilton Depression Rating Scale, Seasonal Affective Disorders version (SIGH-SAD)⁶⁰ (as atypical symptoms in particular respond to light treatment⁶¹) Mania⁶² ratings (to document any clinical induction of manic symptoms by the wake or light interventions) – once weekly for 8 weeks,
- Beck Depression Inventory (BDI)⁵⁷ (as a validated subjective assessment of depression) – once weekly for 8 weeks,
- Beck Anxiety Inventory (BAI)⁵⁸ (as many women with PMDD report anxiety symptoms)⁶³ – once weekly for 8 weeks,
- The Psychological General Well-Being Index (PGWI)⁶⁴ – once weekly for 8 weeks,
- Daily mood self-ratings (DMR)⁵⁴ that include core PMDD symptoms of anxiety and irritability – daily for 8 weeks,
- Expectation form measuring patient expectation for change with the interventions (100 mm line from “much worse” to “much better”) – completed once,
- Horne-Östberg scales to assess morningness and eveningness⁶⁵ – completed once,
- Seasonal Pattern Assessment Questionnaire (SPAQ)⁶⁶ – completed once,
- Pittsburgh Sleep Quality Index (PSQI)⁶⁷ to assess subjective sleep quality – once in month 1 and month 2,
- Visual analogue scale⁶⁸ to assess subjective sleep quality – once in month 1 and month 2,

- Structured Clinical Interview for DSM-IV (SCID)^{51, 52} – completed once to establish diagnosis in evaluation week 8,
- Ovulation testing performed for 7 days starting on menstrual cycle day 10 in month 2 to determine luteinizing hormone surge (LHS). Participants will contact Study Coordinator with their time of first menses (cycle day 1) to determine cycle day 10 and schedule appointment for collecting study forms and equipment,
- Actigraphy will be collected for 10 days starting the day of LHS to monitor baseline sleep, light and activity measures at home,
- Urine collection for 30 hrs performed between days 8-9 after LHS.

Enrollment

Enrollment in the evaluation phase of the study occurs at the time of first screening visit when patients sign a Screening Consent form.

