6.2.4 Treatment Visits

In accordance with the Schedule of Evaluations (section 6.1 above), treatment-related measures will be collected in months 3 and 5 as follows:

- Hamilton: The Hamilton Rating Scale for Depression (HRSD)⁵⁶ (as a validated objective, interview-based assessment of depression). Atypical depression symptoms as part of the Structured Interview Guide for the Hamilton Depression Rating Scale, Seasonal Affective Disorders version (SIGH-SAD)⁶⁰ (as atypical symptoms in particular respond to light treatment⁶¹) Mania⁶² ratings (to document any clinical induction of manic symptoms by the wake or light interventions) – on ovulation night (LSH), daily on LHS+1 – LHS+2 (during intervention) and once after light treatment on LHS+8-9 (post-intervention assessment).
- Beck Depression Inventory (BDI)⁵⁷ (as a validated subjective assessment of depression) – on ovulation night (LSH), daily on LHS+1 – LHS+2 (during intervention) and once after light treatment on LHS+8-9 (post-intervention assessment),
- Beck Anxiety Inventory (BAI)⁵⁸ (as many women with PMDD report anxiety symptoms)⁶³ – on ovulation night (LSH), daily on LHS+1 – LHS+2 (during intervention) and once after light treatment on LHS+8-9 (post-intervention assessment),
- The Psychological General Well-Being Index (PGWI)⁶⁴ – on ovulation night (LSH), daily on LHS+1 – LHS+2 (during intervention) and once after light treatment on LHS+8-9 (post-intervention assessment),

- Daily mood self-ratings (DMR)⁵⁴ that include core PMDD symptoms of anxiety and irritability – collected daily on LHS+0 through LHS+2 (for wake therapy effects) and daily LHS+3 through LHS+10 (for light treatment effects),
- Pittsburgh Sleep Quality Index (PSQI)⁶⁷ to assess subjective sleep quality – once on LHS+8-9 (post-intervention assessment),
- Visual analogue scale⁶⁸ to assess subjective sleep quality – once on LHS+8-9 (post-intervention assessment),
- Ovulation testing performed for 7 days starting on menstrual cycle day 10 in months 3 and 5 to determine luteinizing hormone surge (LHS). Participants will contact Study Coordinator with their time of first menses (cycle day 1) to determine cycle day 10 and schedule appointment for collecting study forms and equipment,
- Actigraphy will be collected for 10 days starting the day of LHS to monitor baseline sleep, light and activity measures at home,
- Urine collection for 30 hrs performed between days 8-9 after LHS.

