6.2.6 Follow-up/Final Evaluation

During final visit, subjects will again perform the Hamilton, BDI, BAI and PGWI ratings (once). They will also complete the Global Assessment of Treatment Effectiveness form. Final evaluation of inclusion/exclusion criteria will be performed at this time.

After completion of the study (final visit), participants will be followed up for 1 month to monitor relapse. The Clinical Rater will telephone the patient at home during the luteal phase, around the same time in the patient's cycle as the post treatment 2 ratings were collected, to collect follow-up mood ratings (Hamilton, BDI, BAI and PGWI).

None of the subjects will be excluded from analysis, and their data will be analyzed according to the randomization scheme. Different hypotheses are included for different phases of the study. All subjects will be included in any baseline analyses regardless of their final study status. In addition to the baseline data, at least one other data point is needed in order to provide a valid estimation of a parameter for change throughout the study. The Random Regression Model was selected due to the flexibility of this method that includes all subjects with any valid data point in the analyses, as opposed to a method that is designed to examine just

the completers, such as a Repeated Measures Analysis of Variance. All subjects will be included in the analyses and we will not focus only on subjects who complete the study. Secondary analyses will be performed on data from completers. Our methods for data analyses include all subjects with any valid data points in the analyses (see Section 9.6. General Approach to Data Handling and Statistical Analyses).

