9. STATISTICAL CONSIDERATIONS

9.1 General Design Issues

The design is a randomized cross-over contrasting LWT+AM bright light vs. EWT+PM bright light administered in the luteal phase of two separate menstrual cycles, and preceded by 2 evaluation months. To lessen the patient's burden, the 1-night EWT or LWT and the following 7-day BWL interventions will be conducted at home, given at a fixed point in each menstrual cycle, from day 1 to 7 after the mid-cycle LH surge. We anticipate that LWT+7 days of AM BWL (vs. EWT+PM BWL) will produce much greater mood benefits and larger physiological responses, than the one-time light pulses used in our earlier phase-shift studies.

The wake therapy and light interventions proposed in this application are based on our previous studies in PMDD and key published experiments by other investigators that indicate that the combined interventions are efficacious in other mood disorders after one week of treatment and maintained at 9-months follow-up. To provide optimal timing of interventions, we will administer wake therapy in the early-night vs. late-night and light pulses in the AM vs. PM at selected times in relation to sleep (within 30 min of waking and 90 min before sleep onset, respectively).

A crossover treatment design is employed to compare LWT+AM BWL vs. EWT+PM BWL responses within the same individual. As wake interventions lose effectiveness after 1 day, and light treatment effects after 3-4 days, we anticipate minimal carry-over effects of the wake plus light interventions administered a month apart. To further ensure no carry-over effects, there will be a month of no-intervention between the 1st and 2nd treatments. Because our previous studies clearly indicated differences between PMDD and NC subjects occurred primarily in the luteal menstrual cycle phase, we will treat during this menstrual cycle phase rather than in the follicular phase.

Hypothesis (H) 1: For PMDD patients in the luteal phase, LWT+AM BWL, compared with EWT+PM BWL, will A) Decrease scores on SIGH-SAD, BDI, BAI, and DMR, and increase global assessment of treatment effectiveness from baseline to post-intervention; B) Phase-advance urinary melatonin timing measures (acrophase, onset and offset time) in relation to clock time and to sleep measures (onset, end time and mid-sleep times); C) The magnitude of the phase-advance (B, above) will correlate with the magnitude of the symptom changes (A, above) by linear regression.

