 - e. Day after LHS (LHS+1) – commence first light treatment (for 7 days)
 - f. LHS+8 → LHS+9 – commence urine collection (30 hrs)
 - g. LHS+11 – equipment, samples and forms are returned to lab
5. Washout (Month 4)
- a. Perform clinical ratings only
6. Treatment 2 (Month 5)
- a. Record CD1 (patient will call Study Coordinator with date and to schedule pre-intervention in-office visit)
 - b. Pre-Intervention Visit – to be completed between cycle days 1 and 10:
 - i. Provide ovulation test kit
 - ii. Provide urine collection kit
 - iii. Provide Actiwatch Spectrum
 - c. Menstrual Cycle Day 10 – commence testing for LHS (7 days of testing)
 - d. Ovulation Day (LHS) – commence actigraphy recording (for 10 days)
 - commence Wake Therapy (1 night)
 - e. LHS+1 – commence first light treatment (for 7 days)
 - f. LHS+8 → LHS+9 – commence urine collection (30 hrs)
 - g. LHS+11 – equipment, samples and forms are returned to lab
7. Final Visit (can be performed at time of item 6.g. above)
- a. Review side effects to treatment and subjective global assessment of treatment effectiveness.
8. Follow-up (luteal phase in the month following Treatment 2)
- a. Perform clinical ratings per telephone.

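### Hypothesis 1.A claims a baseline-to-post treatment difference in the global effectiveness rating, but the rating has no baseline and is scheduled once, after both treatments

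*Combined protocol and SAP*

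**What the plan says.** Section 9.1 states Hypothesis 1.A as a comparison of LWT+AM BWL with EWT+PM BWL that will "Decrease scores on SIGH-SAD, BDI, BAI, and DMR, and increase global assessment of treatment effectiveness from baseline to post-intervention". Section 9.6 assigns Hypothesis 1.A to a random regression with a saturated treatment-by-time structure and gives no other method for the global score.

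On when the score is collected:

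- Section 9.5.2, Secondary Outcomes: "Following both treatment interventions, subjects will complete a visual analog scale-based global assessment of treatment effectiveness".
- Section 6.2.6, on the final visit: "They will also complete the Global Assessment of Treatment Effectiveness form".
- Appendix I, item 7 (Final Visit): "Review side effects to treatment and subjective global assessment of treatment effectiveness". Items 4 and 6, for the two treatment months, do not mention the form.
- Section 6.2.2 introduces its list with "baseline measures will be collected in Evaluation Month 2 as follows"; the global assessment is not on it.
- Section 6.2.4 introduces its list with "treatment-related measures will be collected in months 3 and 5 as follows"; the global assessment is not on that one either.

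On status, section 1.2 puts subjective effectiveness under the secondary objectives, section 9.5.2 lists it as a secondary outcome, and section 9.5.1 does not include it among the primary mood ratings.

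**The concern.** The hypothesis needs two things from this measure: a value before treatment, and a value attributable to each treatment. The collection schedule supplies neither. A rating of how well a treatment worked has no meaning before any treatment has been given, so the missing baseline is not something a visit could repair.

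At stake is whether the trial can report a treatment difference on the one item that asks women directly whether the treatment helped. A rating not taken after Month 3 cannot be recovered later except by recall. If the score was also meant to enter the Hypothesis 1.C correlations, which section 9.6 bases on individual slopes, no slope can be formed from a single point.

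**Working it through.** The plan gives no sample size, power or alpha for this measure, so there is no figure to reproduce. The check is whether the stated contrast is estimable from the scheduled data.

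**Inputs.** Two-period crossover, 40 women (sections 3 and 9.2). Ratings per woman as scheduled: 0 at baseline (6.2.2), 0 in the Month 3 and 5 list (6.2.4), 1 after both treatments (9.5.2, 6.2.6, Appendix I).

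**Step 1: change from baseline.** Change = post minus baseline. With no baseline value the difference is undefined for every woman. Section 6.2.6 itself says that estimating change takes the baseline plus at least one further data point.

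**Step 2: does *both* mean *each*?** The next item in 9.5.2 reads "Following each treatment interventions, subjects will complete an assessment of side effects using the Side Effects Checklist" and names Months 3 and 5. The same list uses the two words differently, and 6.2.6 and Appendix I agree with a single completion. The once-only reading is much the stronger.

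**Step 3: treatment contrast from one overall score.** Let A be LWT+AM BWL and B be EWT+PM BWL. Every woman has had both, so the exposure columns for A and B equal 1 for all 40. A design matrix with mean, period, exposure to A, exposure to B and sequence has rank 2 (mean and sequence). Dropping the two exposure columns leaves rank 2, so they carry no information and A minus B is not estimable.

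The only contrast left is A-first against B-first. Suppose a woman's overall score puts weight w on her last treatment and 1 − w on her first:

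- A-first: (1 − w)A + wB
- B-first: wA + (1 − w)B
- Difference: (1 − 2w)(A − B)

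This is zero at w = 0.5, and otherwise has a sign and size that depend on an unknown w. It is an order effect, not a treatment effect.

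**Step 4: one rating after each treatment.** With 40 woman effects, one period term and one treatment term there are 40 + 1 + 1 = 42 columns. The rank is 42 with the treatment column and 41 without it, so treatment is estimable. If P is the period effect (second minus first), the within-woman difference A minus B has expectation T − P in A-first women and T + P in B-first women. The average of the two is T, the treatment effect. This is a post-treatment comparison; change from baseline remains undefined.

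**Step 5: a single sitting with one scale per treatment.** The documents do not rule this out. The last light session is at LHS+7, and Appendix I allows the final visit at LHS+11 of Month 5. Eligible cycles last 26 to 32 days (4.1). Assuming the surge falls on the same cycle day in each month and no cycle is postponed:

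- Second treatment: 11 − 7 = 4 days after its last session.
- First treatment: 2 × 26 + 4 = 56 days to 2 × 32 + 4 = 68 days.

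The first treatment would be rated after about two months and the second after a few days.

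**The case against.** The strongest reply has four parts.

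**The form is not shown.** It could hold a scale for each treatment, and asking for a judgement once a woman has tried both is a defensible crossover choice. This stands. The loss of the treatment contrast is conditional on a single undifferentiated scale, and a reader should not infer that all 40 women certainly lack a per-treatment score. Nor do the documents show that an overall score would mostly reflect the second treatment. The undefined baseline-to-post change survives either way.

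**Absence from 6.2.4 is weak evidence.** That section and Appendix I both defer to the Schedule of Evaluations in 6.1, which is not legible as extracted: the urine row shows one mark although urine is collected in Months 2, 3 and 5. Nor is 6.2.4 exhaustive, since the daily sleep logs analysed in 9.6 are not listed there. This also stands, and the point does not rest on the table. It rests on the positive statements in 9.5.2, 6.2.6 and Appendix I. If 6.1 does mark Months 3 and 5, those sections contradict it.

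**The measure is secondary.** Sections 1.2, 9.5.1 and 9.5.2 all treat it so, section 1.1 states part A only as improved mood on rating scales, and the power figures in 9.2 do not use it. A reader might infer from section 9.1 that part of the primary endpoint is untestable; the documents do not support that.

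**Side effects are a different case.** A reader might infer that side effects, too, can no longer be attributed to a treatment, because 6.2.4 omits the checklist and Appendix I mentions it at the final visit. But 9.5.2 already requires it 1-2 days after the intervention in Months 3 and 5, Appendix I speaks of a review rather than first completion, and section 7.3 has adverse events recorded as they occur with onset and duration. Loss of attribution is not established; what remains is an omission from one list.

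**Conclusion.** The point holds for the global assessment. The baseline-to-post change named in Hypothesis 1.A cannot be computed for any woman, whatever the form looks like. The LWT+AM BWL versus EWT+PM BWL contrast cannot be estimated if the form yields one overall score. If it has a scale per treatment, a post-only comparison is possible, with the first treatment recalled after roughly 56 to 68 days under the cycle assumptions above.

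The size is one of the five measures listed in Hypothesis 1.A. SIGH-SAD, BDI, BAI and DMR have their own baseline and treatment-month ratings and are unaffected. The plan also disagrees with itself on status, since the measure sits in the main hypothesis in 9.1 and among the secondary outcomes in 9.5.2. This should be corrected before Month 3 data are collected, but it does not threaten the primary mood analysis.

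**What to change.** 1. Add the Global Assessment of Treatment Effectiveness to 6.2.4 at LHS+8-9 in Months 3 and 5, one rating each time, worded to refer to the treatment just completed. Align 9.5.2, 6.1, 6.2.6 and Appendix I.
2. In 9.6, specify a within-woman comparison of the two post-treatment ratings, with terms for treatment and period.
3. In Hypothesis 1.A, delete the baseline reference for this measure and label it secondary there and throughout.
4. As a minor consistency correction, list the Side Effects Checklist in 6.2.4 at the per-treatment timing that 9.5.2 already gives. Light ends at LHS+7, so LHS+8-9 is 1-2 days afterwards.

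The cost is one short extra form in Month 3, at an assessment where women already complete self-ratings; in Month 5 the rating moves forward from the final visit. If the sponsor prefers to keep a single end-of-study rating, the alternative is to remove it from Hypothesis 1.A and report it descriptively, which gives up the treatment comparison.
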